9.4 Provisions to Monitor the Study to Ensure the Safety of Subjects

Automated data quality control checks will be built into the design of the Oncore database, including logic checks and pop up alerts that require the individual entering data to double check any flagged entries. Each month, the Project Coordinator will conduct an audit of 25% of the EMRs reviewed to determine accuracy of the primary and secondary outcome ascertainment. If errors are encountered, the Project Coordinator will notify the PI and all reviewed charts will be assigned for re-review. Data monitoring will include a continuous review of 100% of adverse events by the PI. Progress toward participant enrollment and delivery of arm-specific interventions will be monitored by the Project Coordinator and staff biostatistician on a weekly basis. Study progress and safety will also be reviewed weekly. Updates, including patient recruitment, retention/attrition, and AEs will be provided to the PI following each of these weekly reviews either by phone, email or in person. In addition to weekly updates provided to the PI, the

PI and project coordinator will plan to have biweekly meetings in person. At each meeting, the Project Coordinator will provide the following information: number of participants entering the study, status with respect to meeting recruitment targets, percentage of patients assessed who enter the study, number of drop outs, percentage of patients at each stage of the project, and percentage of assessments completed at each assessment point. Per institutional requirement an Annual Report will be compiled and will include a de-identified list and summary of AEs. In addition, the Annual Report will address (1) whether AE rates are consistent with pre-study assignments (2) whether all participants met entry criteria (3) whether continuation of the study is justified on the basis that additional data are needed to accomplish the stated aims of the study. The IRB and other applicable recipients will review progress of this study on an annual basis.

Data to be collected includes the following: Demographics of participants, HPV test results, clinical follow up outcome (attendance for clinical follow-up among patients with a positive HPV test), time to clinical follow-up for patients with a positive HPV test, self-reported adverse events, accrual numbers and percentages, withdrawals, protocol adherence and stopping rules. Plan for Assuring Protocol Adherence: To ensure compliance with delivery of arm-specific interventions the project coordinator will audit the project database weekly to ensure that trial intervention are being delivered according to the protocol (e.g. that self- sampling kits are mailed out within 3 business days of the telephone recall and that patient navigation is delivered 3-5 business days after mailing out of the self-testing kit) Laboratory Compliance: The Project Coordinator will audit the EMR weekly to ensure that HR-HPV testing is completed on returned kits and that the results are reported in the EMR. The project coordinator will be responsible for notifying and ensuring that the clinical co-investigator [name] reviews HR-HPV positive results and determines a clinical management plan according to the algorithm established per the protocol. Reporting of Adverse Events: Potential adverse events associated with self-sampling are comparable to those associated with standard of care clinic-based screening (e.g. light bleeding, slight cramping). In the research letter, participants will be given a telephone number to call to report injury and other adverse events. Adverse events that are reported will be documented on a reporting form and will be graded according to the Common Terminology Criteria for Adverse Events. Adverse events will immediately be brought to the attention of the PI and reported to the IRB.

An annual report will be compiled and will include the de-identified list and summary of AEs. In addition the Annual Report will address (1) whether AE rates are consistent with pre-study assumptions; (2) whether all participants met entry criteria; (3) whether continuation of the study is justified on the basis that additional data are needed to accomplish the stated aims of the study. While we do not expect any serious unanticipated adverse events to occur, these incidents will be reported to the IRB for immediate review as soon as they are brought to the attention of study staff.

Communication between study staff, patient navigators, and clinical co-investigators ([name] and [name], Medical Chief of Staff) that involves PHI will be conducted through OnCore, secure email, and secure One Drive.

Through a Data Transfer Agreement (DTA), study datasets will be shared with co-investigators at The University of Texas MD Anderson. Transmission of data will be done securely in accordance with the rules and regulations of the Data Transfer Agreement. One Drive is currently used for transmission of PHI as stated above and can also be used for transmission of study datasets, if stipulated in the DTA.

De-identified patient trial data will be sent to investigators at MUSC. MUSC will not be sending data/specimens to MD Anderson. De-identified patient trial data and de-identified specimens will be sent to Rice University. Rice U will not be sending data/specimens to MD Anderson.

De-identified data will be shared with MUSC investigators. Raw data will be shared with MDACC investigators.

A DTA and MTA has been obtained for data transfer between BCM and MDACC. The BCM PI will contact BCM SPO to determine whether a DTA/DUA/MTA is required for the proposed data transfers with Rice University. These agreements will be established if determined necessary by SPO.

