cancers worldwide) to improve risk stratification and determine the appropriate algorithm for clinical follow-up. As is standard, test results will be interpreted as 1) HR-HPV negative, 2) HR-HPV positive and HPV 16/18/45 negative; 3) HR-HPV positive and HPV 16/18/45 positive; or 4) inadequate (due to unsatisfactory sample). Kits that are returned after >30 days will also be considered inadequate.

Test results will be sent via Harris Health secure transmission to co-investigator [name], the study coordinator, and the PN team. Notification of test results and referral for clinical follow-up: HR-HPV positive test results will be communicated on a weekly basis to co-investigator [name]. [name] will be responsible for referring HR-HPV positive women to clinical follow-up. Notification to participants of both negative and positive results will be conducted by the PNs, who will contact participants by telephone within 10 days of the laboratory's receipt of the sample. Participants who are unreachable after 3 telephone attempts on different days/times will be mailed their results by certified mail. Results will be reported as follows: HR-HPV negative women will be told that no high-risk HPV strains were found in their sample. However, since self-sampling is not currently approved for primary screening, women will be advised to attend for clinic-based screening within the next 12 months. [name] is now affiliated with MD Anderson and will continue to provide clinical oversight for the trial and review lab results through the secure Harris Health EMR system. MD Anderson has been added as a site for this study with the BCM IRB. HR-HPV positive. Women who test positive for HR-HPV but negative for 16/18/45 will be referred by [name] to clinic-based screening (Pap/HR-HPV co-testing). They will be asked to make an appointment with their healthcare provider and given clinic contact information. Women who test positive for HR 16/18 will be referred to colposcopy. As is standard practice at Harris Health when screening abnormalities are encountered, women requiring follow-up Pap test screening or colposcopy who have not made an appointment within 30 days of test result notification will receive a telephone call from a PN who will assist them with scheduling an appointment.

Inadequate: Women whose samples were inadequate (due to unsatisfactory sampling or kit returned after >30 days) will be advised to attend for clinic-based screening or mailed a new kit.

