Screening test results will be ascertained within 6 months of randomization. Pap/HR-HPV co-testing results will be ascertained by EMR review. Self-sample HR-HPV test results will be based on laboratory reports. Completion of clinical follow-up will be ascertained by EMR review within 6 months of the date of the screening test result. Completion of clinical follow-up is defined as attendance for colposcopy among participants who had a positive test by clinic-based screening and attendance for colposcopy or subsequent clinic-based screening among those who had a positive test by self-sampling. Additional exploratory outcomes (sub-aim 2) are detection and treatment of cervical precancers (i.e., histologically-confirmed cervical intraepithelial neoplasia grade II or greater [CIN2+]). Precancers will be ascertained by EMR review within 6 months of abnormal screening results and treatment as per ASCCP guidelines will be ascertained within 6 months of the date of diagnosis. Completion of primary care appointments will be ascertained at 6 months, including telehealth appointments.

Study Calendar A – Editable Example				
	Study Timepoints			
	Screening	Telephone survey	Qualitative Interview	Outcomes chart review
Informed Consent	X			
Demographics	X			
Clinical history	X			
Questionnaire		X	X	X
Intervention: Data collection, questionnaires		X	X	X
Adverse Events Reporting	X	X	X	X

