6.2.2 Waiver of Consent

We are requesting a waiver of consent to conduct the chart review to determine subject eligibility.

We are also requesting a waiver of consent for subjects in Arm 1 (control arm). Telephone recalls are standard care in many health systems; additionally: 1) participation involves no more than minimal risk; 2) the waiver will not affect the rights and welfare of participants; and 3) the research could not practically be done without the waiver.

Finally, we are requesting a waiver of consent from subjects in Arms 2 and 3 (intervention arms) who do not complete and return the self-sampling kit. Even though they do not participate in the intervention, we would like to review their medical record to determine if they subsequently attended for clinic-based screening. The following criteria are met: 1) participation involves no more than minimal risk; 2) the waiver will not affect the rights and welfare of participants; and 3) the research could not practically be done without the waiver.

Chart review to determine eligibility: The proposed chart to identify patients who are eligible for participation in the RCT involves only minimal risks to individuals. The risks to privacy are small and the waiver will not adversely affect the patients' privacy rights or welfare. While PHI will be recorded during the chart review, the the database will be stripped of patient identifiers for data analysis.

Subjects enrolled in Arm 1 (control group): Use of PHI for subjects in this groups involves minimal risk. Participants in the control arm receive standard-of-care services (patient recalls) that are already used at Harris Health (based on availability of grant funding) to encourage screening participation among un-/underscreened women. Screening outcomes will be assessed by chart review for participants in this group, but this is not different to what would be done for routine program evaluation purposes.

Subjects enrolled in Arms 2 and 3 (intervention groups): Use of PHI for subjects in this group involves minimal risk. These are participants who declined the self-sampling intervention but may still feel encouraged to participate in standard-of-care clinic-based screening. Screening outcomes will be assessed by chart review.

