7 ADVERSE EVENTS & RISKS

7.1 Adverse Events

Patients will be directed to the PI to report any AEs. Research Information Sheet will be provided to subjects with clear instructions about how to manage these potential but rare adverse events. In the case of pain and bleeding, the symptoms should resolve on their own within a few days.

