7.2 Risks to Subjects

Randomized Controlled Trial For participants in the control arm (Arm 1) there are mild emotional risks from learning or being reminded of being past-due for recommended cervical cancer screening. Additionally, there is risk of potential loss of confidentiality.

For participants in the intervention arms (Arms 2 and 3), there are mild emotional risks from learning or being reminded of being past-due for recommended cervical cancer screening. There are minor physical risks of using the self-sampling device. Specifically, the self-sampling device may be a somewhat uncomfortable to use and may cause a very low level of pain and minor bleeding (spotting) during and/or after use that is caused by a small scratch to the vagina or cervix. These risks are minimal with no such events being reported in previous studies. In the Research Information Sheet, we provide subjects with clear instructions about how to manage these potential but rare adverse events. In the case of pain and bleeding, the symptoms should resolve on their own within a few days.

In the Research Information Sheet, participants are told that pregnant women should not use the collection device. In the event that they find out later that they were pregnant when they used the device, they are instructed to inform their OB/GYN and provided the number for BCM OB/GYN if they do not have an OB/GYN.

The Aptima transport medium is non-hazardous and non-flammable. Detailed instructions for safely returning the vial to the laboratory are described in the instructional brochure. After the vial has been tightly capped, participants are instructed to place the capped vial into the provided biohazard bag and seal the bag using the Ziploc mechanism. In accordance with shipping rules, this inner receptacle (biohazard bag) must have an inner or outer absorbent material capable of absorbing the volume of the liquid. Thus a Green Z Drop-in Pac will be included within each biohazard bag. This will ensure that any inadvertent spillage during shipping will be absorbed.

There are potentially emotional risks of testing for HPV, especially among women who learn they are positive for high-risk HPV. There is also a small chance that individuals who test negative for high-risk HPV are in fact infected. Finally, there is a risk of potential loss of confidentiality.

*While the study involves only minimal risk, the funding agency requested a Data Safety Monitoring plan (attached in Section S).

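### Kit-related adverse events are described as participant-initiated reports with no defined denominator, so minor events are likely to be under-counted and the annual check of AE rates has a weak basis

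*Combined protocol and SAP*

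**What the plan says.** The narrative describes reporting that starts with the participant. Section 9.4: "In the research letter, participants will be given a telephone number to call to report injury and other adverse events". Section 7.1: "Patients will be directed to the PI to report any AEs". Section 3.1 places the reporting number in the Research Information Sheet, which is mailed with the kit. Section 9.4 lists the data item as "self-reported adverse events". No section has staff ask about AEs.

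The calendar in Section 6.1, which is headed as an editable example, has a row "Adverse Events Reporting" marked at screening, telephone survey, qualitative interview and outcomes chart review. The survey content in Sections 3.2 and 3.4 and the chart-review content in Section 3.1 include no AE item. Section 3.1 also extends AE monitoring to 90 days after a participant goes off-study and gives no method.

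AE rates are put to use: the Annual Report is to address "1) whether AE rates are consistent with pre-study assumptions" and whether continuing the study is justified. The nearest thing to a benchmark is in Section 7.2: "These risks are minimal with no such events being reported in previous studies". No numerical rate is given.

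A contact with kit returners already exists. Section 3.1: "Notification to participants of both negative and positive results will be conducted by the PNs". The call is to be made within 10 days of the laboratory's receipt of the sample, and women not reached after three attempts are sent results by certified mail.

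**The concern.** Spontaneous reporting tends to miss minor events, and minor events are what this protocol expects: light bleeding, slight cramping, some discomfort. Sections 7.1 and 7.2 say the information sheet explains how to manage such events and that symptoms should clear within a few days, which gives a woman little reason to telephone.

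A rate also needs a denominator. Women who return a kit are known users. Women who tried the kit but did not return it are not identified systematically, and no section says whether the AE rate is per kit mailed, per kit returned or per kit used.

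At stake is the annual safety judgement, not the primary outcome. A low count could mean few events or few reports, and the plan as described gives no means of telling which.

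**Working it through.** The plan states no AE rate, so there is no figure to reproduce. The check sets out who could be asked, then illustrates how much a low count would tell.

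**Inputs from the documents**
- Arm size: 756 (Section 4), so kits mailed in Arms 2 and 3 = 2 × 756 = 1,512. Adding the supplement's 60 + 60 gives 1,632.
- Kit return in earlier trials: 10–39% (Section 1.2).
- Telephone survey: 272 women, plus 40 in the supplement (Section 4). HR-HPV-positive women needing follow-up are excluded (Section 4.2).

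**Who could be asked**
- Returners, for whom a results call would be attempted: 1,512 × 0.10 = 151 to 1,512 × 0.39 = 590. With the supplement: 163 to 636.
- Non-returners, whose kit use is unknown: 1,512 − 590 = 922 to 1,512 − 151 = 1,361.
- Survey coverage of kit recipients: 272/1,512 = 18%. With the supplement: 312/1,632 = 19%. Even if the survey asked about AEs, about four in five recipients would depend on self-report or chart review.

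**How informative a low count would be (assumed values)**

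Neither the true AE rate p nor the fraction reported c is in the documents. Apparent rate = p × c; expected reports = n × p × c; chance of no report = (1 − p × c)^n, with n the number of returners.

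| p | c | p × c | Expected reports, n = 151 / 590 | Chance of none, n = 151 / 590 |
|---|---|---|---|---|
| 2% | 10% | 0.2% | 0.3 / 1.2 | 74% / 31% |
| 5% | 10% | 0.5% | 0.8 / 2.9 | 47% / 5% |
| 5% | 25% | 1.25% | 1.9 / 7.4 | 15% / 0.1% |
| 5% | 50% | 2.5% | 3.8 / 14.7 | 2% / under 0.1% |
| 10% | 10% | 1.0% | 1.5 / 5.9 | 22% / 0.3% |

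For example, (1 − 0.005)^151 = 0.47 and (1 − 0.005)^590 = 0.05. With low reporting and few returners, an empty AE list says little. With half of events reported, some would very probably appear.

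**Opportunity to report in the two kit arms**

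Under Section 3.1, Arm 3 women get a navigation call 3–5 days after mail-out. Those who intend to self-sample but whose kit has not arrived get up to three telephone reminders. Arm 2 has neither, so Arm 3 has more occasions on which an event could be mentioned.

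**The case against.** The strongest reply is that this is a minimal-risk intervention, AEs are not a trial outcome, and spontaneous reporting with weekly safety review is a legitimate choice. The Data Safety Monitoring Plan, data forms and questionnaires are attachments outside the reviewed text and may already contain AE questions. Both points stand: they limit the weight of the concern and make the remedy conditional. They do not supply the missing denominator or reconcile the calendar with the narrative.

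A reader might also infer more than the documents support:

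- *A phone call from the participant is the only source of AEs.* The Section 6.1 calendar marks other time points. What is missing is the method at those points.
- *Non-returners are counted as unexposed.* Section 6.2.2 does say of them "These are participants who declined the self-sampling intervention", but in order to justify a consent waiver. No AE rule excludes them, every kit recipient is given the number, and some non-returners are surveyed in both arms.
- *A biased comparison between arms is planned.* None is. Arm 1 receives no kit, and the unequal contact between Arms 2 and 3 is a caution for anyone who later compares them.
- *Navigators speak to every returner.* They attempt to. Unreachable women get certified mail, and the notification sentence names only negative and positive results.
- *The annual check would pass whatever the true rate.* The illustration contradicts this: at an assumed 5% rate with 50% reporting, the chance of no report is about 2% or less.

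**Conclusion.** The point holds in a limited form. The stated method is passive, the method at the calendar time points is not given, and no denominator of kit users is defined. Under-counting of minor events is the likely direction, but its size is unknown: the 2–10% event rates and 10–50% reporting fractions above are assumptions. The check against pre-study assumptions therefore rests on a weak count, an undefined denominator and no numerical benchmark.

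This is worth correcting because the remedy is inexpensive and uses contacts already planned. It does not threaten the primary analysis. The conclusion rests on the text reviewed; if the attached monitoring plan or forms already ask about AEs, what remains is to say so in Section 9.4 and define the denominator.

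**What to change.** 1. In Sections 3.1, 6.1 and 9.4, add one short scripted question, identical in Arms 2 and 3, to the results call: any pain, bleeding or injury with the kit, and pregnancy at the time of use. State whether contacts about inadequate samples are included.
2. In the telephone survey, ask non-returners whether they tried the kit and stopped.
3. In Section 9.4, define the AE denominator as known kit users, and report solicited and spontaneous events separately. Show events from surveyed non-returners on their own, since they come from a sample.
4. Reconcile the Section 6.1 calendar with Section 9.4: state how AEs are obtained at the survey, interview and chart review, and during the 90 days off-study.
5. If the attached plan or forms already contain such questions, cite them in Section 9.4 in place of items 1 and 2.

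The cost is a short addition to a call and a survey already planned, with no new contact. Women not reached by telephone would still be missed. More minor AEs would be recorded and sent to the IRB, and the reported AE rate may look less favourable.

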9.5 Sharing of Results with Subjects

HPV test results will be recorded in subject's Harris Health medical records. These can be accessed by both the subject and her doctor. Providers involved in clinical follow-up (i.e., colposcopy or follow-up Pap) will also receive the results. Other providers with access to the electronic medical record can access test results, but will not be notified of them.

Given the parallel accrual of participants to each arm of the study and the long follow-up time needed to ascertain screening outcomes among participants randomized to each arm, we do not have sufficient time in the project period to cross-over control group participants to either of the intervention arms. We thus do not think it is appropriate to give control group participants information of self-sample HPV testing, which is not regularly available at Harris Health. However, all participants, including those in the control arm, will receive some type of intervention (specifically patient recall in the control arm), which is expected to increase their participation in cervical cancer screening.

